8.3 Confidentiality

All data and records generated during this study will be kept confidential in accordance with CHOP’s Institutional policies and HIPAA on subject privacy. Neither the Investigator nor other site personnel will use records and/or data collected for any purpose other than conducting the study.

The following steps will be taken to maintain confidentiality: (1) subject identity will be coded using numbers keyed to a master list; (2) coded data will be entered directly into files that will be password protected, (3) all project staff will be trained in the importance of confidentiality, and will certify in writing to protect subject confidentiality; and (5) if the results of the study are published, data which might reveal the identity of any particular subject will be disguised. Subjects will be informed about the limits of confidentiality (e.g., in cases in which a subject is in danger to themselves or others). No identifiable data will be retained or used for future studies. The investigator will obtain a data use agreement between the provider (the PI) of the data and any recipient researchers (including others at CHOP) before sharing a limited dataset (PHI limited to dates and zip codes).

8.4 Regulatory and Ethical Considerations

8.4.1 Risk Assessment

This is a low-risk study. Data collection involves contact with all participants either remotely over the phone or in person in clinic. As to be expected following the receipt of a new cancer diagnosis or relapse, the education and information related to cancer and treatment that is delivered via DECIDES may increase distress for AYA and caregiver(s). All participants will be informed of this risk prior to participation and will be informed of the right to discontinue participation if they are uncomfortable with the study. If participants become upset or report clinically significant levels of depression and/or anxiety (as defined by norms on the PROMIS scales), [name] (clinical psychologist, Director of Psychosocial Services for the Cancer Center, and PI) will assess the level of distress of the

patient and determine the need for additional psychosocial support. If additional psychosocial support is needed, [name] will initiate follow-up for the patient's social worker for further assessment and intervention. There is also a slight risk of breach of privacy and confidentiality, as with all studies, despite our very careful safeguards to protect data as described above. If required by law, confidential information may be revealed.

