Satisfaction with Decision Scale: This is a valid and reliable 6-item instrument that measures patient satisfaction with a health care decision. The scale provides an efficient measure to evaluate decision-assisting technologies or patient-provider interactions aimed at involving patients in decision-making. Higher scores indicate higher satisfaction with the decision that was made.⁽⁶⁶⁾

Decision Self-Efficacy Scale: This is a valid and reliable 11-item instrument that measures self-confidence in one's abilities in decision-making (including shared decision-making). Items are rated on a 5-point scale, ranging from "not at all confident" (0) to "very confident" (4). Higher scores indicate higher self-efficacy.⁽⁶⁷⁾

Decision Regret Scale: This is a valid and reliable 5-item instrument that measures distress or remorse after a (health care) decision. Items are rated on a 5-point scale, ranging from strongly agree (1) to strongly disagree (5). Items 2 and 4 are reverse coded so that for each item, a higher score will indicate more regret.⁽⁷²⁾

PROMIS Profile: 25, 29, and Parent-Proxy The PROMIS measures assesses physical function mobility, depressive symptoms, fatigue, peer relationships, pain intensity, and pain interference. The PROMIS Pediatric Profile (25 items) is intended for use with those under age 18; the PROMIS Profile (29 items) is intended for use with those over age 18; and the PROMIS-Parent Proxy Profile (25 items) is a parent-report measure.⁽⁹⁶⁻⁹⁸⁾

Distress Thermometer: The Distress Thermometer is from the National Comprehensive Cancer Network (NCCN) Practice Guidelines in Oncology for Distress Management. It is an illustration (thermometer) used with patients to rate the number that best describes how much distress they have been experiencing in the past week, ranging from "no distress" (0) to "extreme distress" (10).

Affective Slider (AS): This is a digital self-reporting tool composed of two slider controls for the quick assessment of arousal (top) and pleasure (bottom) on a continuous scale. The

AS does not require written instructions. The scale is intentionally displayed using a neutral chromatic palette to avoid bias in rating (due to emotional connotation of colors). ⁽⁸⁷⁾

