5.3 Semi-Structured Qualitative Interview

A semi-structured, qualitative interview guide designed by the study team for use with AYA and caregiver(s) (assigned to DECIDES or DECIDES + coach), and oncology health care providers. The purpose of the interview is to obtain further information from participants about the process of treatment decision-making and their experience using DECIDES, the decision aid. Participants will be interviewed by a study team member via remote video conference software (Microsoft Teams). All interviews will be audio and/or video recorded and professionally transcribed (by a CHOP-approved vendor with a BAA in place), and the interview data will be analyzed.

Table 1. Measures

Construct	Measure	Administration	
		T1	T2
Demographics	Electronic Health Record; AYA/Caregiver Self-Report	AYA, CG	
Treatment Intensity	Intensity of Treatment Rating Scale (ITR-3) ⁽⁹⁹⁾	PR	
Acceptability ^(D)	Acceptability of the Decision Aid ⁽⁶⁾		AYA, CG
Usability ^(D)	The Systems Usability Scale ^(36,71)		AYA, CG, PR
AYA Involvement in Shared Decision-Making	Control Preferences ^(74,75)		AYA, CG
	Physician Decision-Making Scale ⁽¹⁰⁰⁾		AYA, CG
	Shared-Decision Making Questionnaire (SDM-Q-9) ⁽⁹⁴⁾		AYA, CG
Knowledge	AYA Hope Survey: Information Need ^(76,77)	AYA, CG	
	Knowledge of Clinical Trials ⁽⁶⁴⁾	AYA, CG	AYA, CG
Attitudes to Clinical Trials	Pediatric Research Participation Questionnaire	AYA, CG	AYA, CG
Alignment of Decision with Values	(PRPQ) ^(15,16)		AYA, CG
Decision-Making	Certainty	Decisional Conflict Scale ⁽⁶⁵⁾	AYA, CG
	Satisfaction	Satisfaction with Decision Scale ⁽⁶⁶⁾	AYA, CG
	Self-Efficacy	Decision Self-Efficacy Scale ⁽⁶⁷⁾	AYA, CG
	Regret	Decision Regret Scale ⁽⁷²⁾	AYA, CG
Health-Related Quality of Life	PROMIS Parent Proxy Profile-25 ⁽⁹⁸⁾	CG	CG
	PROMIS Pediatric Profile-25 ⁽⁹⁷⁾	AYA (15-17)	AYA (15-17)
	PROMIS-29 Profile ⁽⁹⁶⁾	AYA(18-24)	AYA(18-24)
*Distress	Distress Thermometer ⁽⁷³⁾	AYA, CG	AYA, CG
*Valence and Arousal	Affective Slider ⁽⁸⁷⁾	AYA, CG	
*Awareness of Feeling Emotions	Affective Orientation (AO15) ⁽⁸⁸⁾	AYA, CG	
*Developmental Status	Developmental Task Questionnaire ^(89,92)	AYA	
*Psychosocial Maturity	Consideration of Future Consequences ⁽⁹⁰⁾	AYA, CG	
	Psychosocial Maturity Inventory ⁽⁹⁵⁾	AYA	
	Emotion Regulation Questionnaire ⁽⁹¹⁾	AYA, CG	
*Problem-Solving	Family Assessment Device (FAD): Problem-Solving ⁽⁹³⁾	AYA, CG	
Semi-Structured Qualitative Interview ^(D)	DECIDES Interview Guide		AYA, CG, PR

* = Covariate

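### Section 8.4.1 names caregiver distress as a study risk, but words its response for the patient, and its PROMIS trigger cannot register a caregiver's own distress

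*Combined protocol and SAP*

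**What the plan says.** Section 8.4.1 states that the information delivered through DECIDES "may increase distress for AYA and caregiver(s"). It then sets a rule with two triggers, both worded for participants: becoming upset, or a score trigger for those who "report clinically significant levels of depression and/or anxiety (as defined by norms on the PROMIS scales").

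The response has two steps. The psychologist (also the principal investigator) is to assess the level of distress of the "patient and determine the need for additional psychosocial support". If support is needed, that person "will initiate follow-up for the patient's social worker for further assessment and intervention".

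On measurement, section 5.2 says the "PROMIS-Parent Proxy Profile (25 items) is a parent-report measure". Table 1 lists the "PROMIS Parent Proxy Profile-25" for caregivers at T1 and T2. The other two PROMIS forms go to AYA aged 15-17 and AYA aged 18-24. Table 1 also gives the Distress Thermometer to both AYA and caregivers at T1 and T2, marked as a covariate. Section 5.2 describes it as a tool to "rate the number that best describes how much distress they have been experiencing in the past week". Section 8.4.1 does not mention it.

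**The concern.** The stated risk and the trigger both include caregivers, but neither response step names them. A coordinator who follows the text literally after a caregiver becomes upset would arrange an assessment of the AYA.

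The score trigger has a further gap. A caregiver's PROMIS answers describe the AYA, so a severely distressed caregiver of an AYA who is coping would not reach it. The one caregiver self-report of distress collected at both time points is not connected to the rule.

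At stake is whether a safety rule works for everyone it is meant to cover. Nothing inferential depends on it.

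**Working it through.** The plan gives no figure to reproduce, so the main check is a comparison of texts.

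**1. Who is covered at each stage**

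| Element | Source | AYA | Caregiver |
|---|---|---|---|
| Stated risk of distress | 8.4.1 | yes | yes |
| Trigger: becomes upset | 8.4.1 | yes | yes |
| Trigger: PROMIS score for own distress | 8.4.1 with Table 1 | yes | no |
| Step 1: assessment of distress | 8.4.1 | yes | not named |
| Step 1: decision on additional support | 8.4.1 | no recipient named | no recipient named |
| Step 2: referral | 8.4.1 | patient's social worker | no route named |

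**2. Does patient mean the AYA?** Section 5.1 speaks of AYA patients, and the Control Preferences entry in 5.2 sets patient against caregiver. Usage is not strict: section 8.1.1 speaks of assigning patients to groups, although section 3.1.2 randomizes family units.

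**3. Does the proxy form rate the AYA?** The documents do not say so outright. It follows from the form's name, its pairing with the 25-item pediatric profile in 5.2, and the title of its cited source, which concerns pediatric proxy-report item banks.

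**4. Do other sections supply a response?** Sections 7.1 and 7.2 cover adverse-event monitoring and IRB reporting. Section 8.3 covers the limits of confidentiality. The coach sessions (4.1.3) and interviews (4.1.5) are points of contact. None states a support step for a distressed caregiver.

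**5. How many scores would a flag screen?** Inputs: at most 65 families, 50 evaluable (3.2.2); allocation 1:2:2, so the website arms hold 4/5 of families (8.1.1); half of AYA expected to be 18 or older (8.1.1); adult AYA may enrol alone (3.3). Let n be families and c the mean number of caregivers per family. The value of c is an assumption.

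- T2 scores in the website arms = n × 4/5 × c
- T1 plus T2 scores in all arms = 2 × n × c

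| Assumed mix | c | T2, website arms (n = 65 / 50) | T1 + T2, all arms (n = 65 / 50) |
|---|---|---|---|
| Every adult AYA alone, each minor with one caregiver | 0.5 | 26 / 20 | 65 / 50 |
| All dyads | 1 | 52 / 40 | 130 / 100 |
| All triads | 2 | 104 / 80 | 260 / 200 |

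The n = 65 figures assume that every enrolled family is randomized and completes each form.

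**6. Which scores could reflect DECIDES?** T1 precedes randomization, and Usual Care does not receive the website. The relevant share is 0.8nc / 2nc = 40%, whatever the mix. The other 60% of an all-arm, two-time-point screen could not reflect the website.

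**The case against.** The best defence is that the paragraph is loosely drafted but workable. The trigger is for participants, the decision on additional support names no recipient, and the referral step says whose social worker is contacted, not who is then helped. A psychologist would naturally respond to whoever became upset, through the social worker attached to the family. The PROMIS trigger also has a coherent reading: it screens AYA by self-report and parent report, while the upset trigger covers everyone. The protocol nowhere undertakes to score-screen caregivers for their own distress.

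There are also real chances to notice an upset caregiver. Section 8.4.1 says "Data collection involves contact with all participants either remotely over the phone or in person in clinic". The coach reviews the website in person and guides the values exercise with AYA and caregivers both apart and jointly. Both website arms have an interview after T2.

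Much of this stands. A reader might infer that caregivers have no protection at all. The documents do not support that, given the upset trigger, the risk disclosure, the right to stop, and adverse-event monitoring. A reader might also infer that caregivers must be score-screened in every arm at both time points. That goes beyond the risk that 8.4.1 describes, since 60% of those scores could not reflect DECIDES.

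What the defence does not supply is a sentence saying what happens for the caregiver. Noticing distress also depends on contact: T1 and T2 may be completed from an emailed link (4.1.2, 4.1.4), and the DECIDES arm uses the website independently (3.1.2).

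**Conclusion.** The gap is real and minor. Followed as written, 8.4.1 states no action for a distressed caregiver, and its score trigger cannot register a caregiver's own distress. The second part rests on the inference that the proxy form rates the AYA, which is well supported but not spelled out.

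No estimate of harm is possible, because the documents give no caregiver distress rate and no cut-off. The only quantity that can be sized is the screening load: about 26 to 104 T2 scores in the website arms at the cap, given the assumed family mix.

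It would be wrong to conclude that a flag would catch website-related distress early. T2 falls about six weeks after randomization and asks about the past week, and a high score there could equally reflect the illness. The gain is a systematic check alongside the AYA PROMIS scores. Nor does the gap bear on the trial's results.

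**What to change.** In section 8.4.1:

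- Replace patient with participant in the assessment step.
- Name a referral route for caregivers alongside the patient's social worker.
- Add a REDCap flag on the caregiver Distress Thermometer, at minimum at T2 in the DECIDES and DECIDES + coach arms, with a cut-off set by the study's clinicians. Extending it to T1 or to Usual Care is optional. It would pick up distress around diagnosis or relapse, and at the cap would raise the scores screened to between 65 and 260.

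The cost is a short wording change, an agreed caregiver route, and one flag on data already collected, with no new instrument or visit. The downside is that the psychologist role already assigned must review flagged scores. Their number is unknown and could be substantial, because families enrol within six weeks of diagnosis or relapse, when 8.4.1 itself expects distress.

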8.4.2 Potential Benefits of Trial Participation

This research does not offer direct medical or psychological benefits to participants. Participation in this study may indirectly improve AYA and caregivers understanding of cancer, cancer treatments (including clinical trials), and involvement in treatment decisions. The knowledge gained from this study may help researchers determine if the DECIDES website is helpful for AYA, caregivers, and oncology health care providers that are working together to make decisions about cancer treatment.

8.4.3 Risk-Benefit Assessment

As the risks of the research are appropriately characterized as "minimal risk", they are reasonable in spite of the anticipated lack of direct medical or psychological benefit to subjects. The potential benefits from knowledge gained through this study and the indirect benefits of helping newly diagnosed or relapsed AYA, caregiver(s), and oncology health care providers making treatment decisions in the future outweigh the minimal risks associated with participation.

8.5 Recruitment Strategy

Oncology health care providers and the psychosocial services team in the Division of Oncology at the Children's Hospital of Philadelphia will assist in the identification of potentially eligible patients newly diagnosed with leukemia/lymphoma, solid tumor, or brain tumor during weekly team meetings. Potentially eligible AYA patients will be referred to the DECIDES study team. If AYA and caregiver(s) meet all eligibility criteria, they will be invited to participate in the study. Informed consent/assent for AYA and caregiver participation will be obtained by phone or in-person during an outpatient oncology clinic visit or inpatient hospital stay.

Following AYA and caregiver study participation, the study team will contact their oncology health care provider and if they meet all eligibility criteria, they will be invited to participate in the study.

Recruitment and enrollment will be tracked using a password protected Excel spreadsheet.

8.6 Informed Consent/Assent and HIPAA Authorization (AYA/Caregivers)

Informed consent/assent will be obtained from AYA and caregiver(s) prior to the beginning of the study during outpatient visits, inpatient admissions, or verbally by phone. A study team member will discuss the procedures and consent forms with potential participants individually. In order to assure that the potential participant understands the study, the team member will review the consent, in its entirety, with the AYA and their caregiver(s) and will encourage them to ask questions throughout the process. The individuals will also be reminded that participation is voluntary and will not affect their care. There are no time

constraints on the consent process. The potential participants will be allowed to take as much time as they need to ask questions and decide if they would like to participate.

If consent/assent is being conducted in-person and the potential participant agrees to participate, the In-Person Signature Page of the consent forms will be signed and dated by the potential participant and the research team member and stored in a regulatory binder maintained by the study coordinator. A copy of the consent forms will be provided to the participant for their records.

8.6.1 Consent with Waiver of Documentation

If consent/assent is being conducted over the phone, we will use Consent with Waiver of Documentation (verbal consent/assent). The study team will complete the Documentation of Consent Page of the consent form, which will be stored in a regulatory binder maintained by the study coordinator. A digital or paper copy of the verbal consent form will be provided for participants' records. Additionally, AYA who are 17 at time of consent and turn 18 during the study period will be re-consented. At the start of the semi-structured qualitative interview, a re-consent conversation will be audio and/or video-recorded to confirm that AYA/caregiver(s) agree to recording of the interview).

8.7 Informed Consent (Oncology Health Care Providers)

Informed consent will be obtained from oncology health care providers of enrolled AYA and caregiver(s). A study team member will discuss the procedures and consent forms with potential participants individually. In order to assure that the potential participant understands the study, the team member will review the consent, in its entirety, and will encourage them to ask questions throughout the process. The individuals will also be reminded that participation is voluntary and will not affect their employment or performance evaluation, and their responses will not be shared with their supervisors. There are no time constraints on the consent process. The potential participants will be allowed to take as much time as they need to ask questions and decide if they would like to participate.

If consent is being conducted in-person and the potential participant agrees to participate, the In-Person Signature Page of the consent forms will be signed and dated by the potential participant and the research team member and stored in a regulatory binder maintained by the study coordinator. A copy of the consent forms will be provided to the participant for their records. At the start of the semi-structured qualitative interview, the re-consent conversation will be audio and/or video-recorded to confirm that oncology health care providers agree to recording of the interview.

8.7.1 Consent with Waiver of Documentation

If consent is being conducted over the phone, we will use Consent with Waiver of Documentation (verbal consent). The study team will complete the Documentation of Consent Page of the consent form, which will be stored in a regulatory binder maintained by the study coordinator. A digital or paper copy of the verbal consent form will be provided for participants' records. At the start of the semi-structured qualitative interview, the re-consent conversation will be audio and/or video-recorded to confirm that oncology health care providers agree to recording of the interview).

8.8 Payment to Subjects

8.8.1 Families (AYA and Caregivers)

To compensate for their time and effort, AYA and caregiver(s) will be paid as a single-family unit via a pre-loaded bank card (hereafter referred to as a ClinCard) or an Amazon e-gift card. Per Clinical Trials Financial Management policy, the ClinCard will be given in person or mailed to families after they are enrolled in the study, or an Amazon e-gift card will be delivered electronically. If the ClinCard is sent via mail, families will be instructed to contact the study coordinator (via phone/email) to confirm receipt of the ClinCard before funds are disbursed. If the ClinCard is delivered in person, families will be asked to provide their signature as confirmation of receipt. Families that receive an Amazon e-gift card via email will be asked to confirm receipt of the e-gift card with the study coordinator. Both confirmation of ClinCard receipt and stipend payments will be tracked in an Excel file (managed by the study coordinator). Families will receive the following stipend amounts at the following time points, based on group assignment:

Families randomized to Usual Care will receive \$50 across two time points.

- Time Point 1: \$25 after completion of the baseline assessment.
- Time Point 2: \$25 after completion of the post-intervention assessment

Families randomized to DECIDES will receive \$70 across three time points.

- Time Point 1: \$25 after completion of the baseline assessment
- Time Point 2: \$25 after completion of the post-intervention assessment
- Time Point 3: \$20 after completion of the semi-structured qualitative interview

Families randomized to DECIDES + coach will receive \$70 across three time points.

- Time Point 1: \$25 after completion of the baseline assessment
- Time Point 2: \$25 after completion of the post-intervention assessment
- Time Point 3: \$20 after completion of the semi-structured qualitative interview

8.8.2 Oncology Health Care Providers

Oncology health care providers will not be compensated for their participation in the study.

9 PUBLICATION

Results of the study will be disseminated via conference abstracts and peer reviewed journal publications.

